	3.4 Pregnancy Reporting						
13.	· · · · · · · · · · · · · · · · · · ·						
14 14.		32					
14. 14.	• •						
	Data Management						
	Translational research or sub-trial – not applicable						
	Protocol/GCP non-compliance						
	End of Trial definition						
	Archiving						
	Regulatory Considerations						
20.							
20.	,						
20.	· · · · · · · · · · · · · · · · · · ·						
	Trial management						
	Quality Control and Assurance						
22.	5						
22.	· · · · · · · · · · · · · · · · · · ·						
	Public Involvement and Engagement						
24	Publication Policy	38					

25 Milestones	38
26 References	39

Glossary of abbreviations

CA Competent Authority

ICF Informed Consent Form

CI Chief Investigator

CTA Clinical Trials Authorisation
CTR Centre for Trials Research

CTU Clinical Trials Unit
CU Cardiff University
DEX Dexamethasone

DSUR Development Safety Update Report

EudraCT European Clinical Trials Database

GCP Good Clinical Practice

GDPR General Data Protection Regulations

GP General Practitioner **IC** Informed consent

ICH International Conference on Harmonization

IEC Independent Ethics Committee
IMP Investigational Medicinal Product

ISF Investigator Site File

ISRCTN International Standard Randomised Controlled Trial Number

MA Marketing Authorisation

MedDRA Medical Dictionary for Regulatory Activities

MHRA Medicine and Healthcare products Regulatory Agency
mNCA Model Agreement for Non-Commercial Research

NHS National Health Service
PI Principal Investigator

PIS Participant Information Sheet

QA Quality Assurance

R&D Research and Development
REC Research Ethics Committee

RGF Research Governance Framework for Health and Social Care

ROM Romiplostim

SAE Serious Adverse Event
SAR Serious Adverse Reaction

SPC Summary Product Characteristics
SOP Standard Operating Procedure

SSA Site Specific Assessment

SUSAR Suspected Unexpected Serious Adverse Reactions

TMF Trial Master File

1 Amendment History

The following amendments and/or administrative changes have been made to this protocol since the implementation of the first approved version.

Amendment No.	Protocol version no.	Date issued	Summary of changes made since previous version
N/A	1.0	TBC	None – first version
N/A	2.0	TBC	Second version - added Section 2.5 Travel Expenses in response to REC review conducted 01/08/2023.
			Amended version number and date on front page and footers.
			Amended electronic authorisation dates on authorisation page.
			Amended Table of contents to capture changes in page numbering.

2 Synopsis

[figure not shown]
Short title	RODEX: A multicentre, randomized, open-label study of romiplostim plus dexamethasone vs dexamethasone in patients with newly diagnosed primary immune thrombocytopenia					
Acronym	RODEX					
Clinical phase	Phase III					
IRAS number	1007244					
EudraCT ref	2021-00690-22					
ISRCTN ref	TBC					
IRAS number	1007244					
Funder	Andalusian Public Foundation for Health Research Management of Seville (FISEVI), Spain. IMP and distribution provided for free by the drug manufacturer, Amgen.					
CTR Study Number	1227					
Trial design	Open label, randomised, Phase 3 study to compare romiplostim plus dexamethasone vs dexamethasone alone in terms of sustained response off any ITP treatment in adult subjects with newly diagnosed ITP.					
Trial participants	Adult patients with newly diagnosed ITP and a clinical indication for first line treatment					
Planned sample size	Total: 126; UK (England, Wales and Scotland): 26+					
Planned number of sites	UK: 10-15					
Duration:	Total: 36 months Treatment: Up to 2 years Follow-up: Up to 1 year from date of last dose of IMP First patient inclusion: Last quarter 2022 Last patient inclusion: First quarter 2024 Subject participation duration: 24 months					
Inclusion criteria	 ≥18 years old at time of informed consnet New diagnosis of primary ITP Platelet count <30x10⁹/L or ITP with platelet count <50x10⁹/L and concomitant bleeding symptoms Serum creatine concentration ≤1.5 mg/dL 					
Exclusion criteria	 WHO performance status >2 Previous therapy with rituximab (within 3 months previous of study enrollment), corticosteroids or therapy with other immunomodulating agents within 1 month before enrolment; prior use of hematopoietic analogs or fostamatinib for any other reason than ITP three months before enrolment. Previous use of romiplostim, PEG-recombinant human (rHu) 					
	megakaryocyte growth and development factor, eltrombopag, recombinant human antithrombopoietin (rHuTPO), or any platelet-producing agent for three months prior to enrolment. 4) Alkylating agents within 8 weeks before the screening visit or anticipated use during the time of the proposed study.					

- 5) Splenectomy within 3 months of the screening visit or planned splenectomy during study period.
- 6) Abnormal renal function (serum creatinine > 1.5 mg/dL).
- 7) Active hepatic disease evidenced by alanine aminotransferase [ALT] or aspartate aminotransferase [AST] levels >5 times the upper limit of normal (it will only be necessary to determine one of the two transaminases).
- 8) Severe chronic liver disease as evidenced by, but not limited to, any of the following: International Normalized Ratio (INR) > 1.4, hypoalbuminemia, portal vein hypertension including presence of otherwise unexplained splenomegaly and history of esophageal varices.
- 9) Patients with known IgM seropositive tests for cytomegalovirus and/or Epstein-Barr virus in the previous month.
- 10) Patients with an active viral infection at screening for Hepatitis B Virus (HBV), Hepatitis C Virus (HCV) or detectable virus charge of HIV.
- 11) Intolerance to dexamethasone.
- 12) History of a bone marrow stem cell disorder.
- 13) Active or prior malignancy except adequately treated (i.e., complete surgical excision with negative margins) basal cell carcinoma.
- 14) History of Helicobacter pylori by urea breath test or stool antigen test within 6 months of enrollment, if available.
- 15) History of myelodysplastic syndrome, systemic lupus erythematosus, or autoimmune cytopenia.
- 16) History of antiphospholipid antibody syndrome.
- 17) History of disseminated intravascular coagulation, hemolytic uremic syndrome, or thrombotic thrombocytopenic purpura.
- 18) History of deep or superficial venous thromboembolism in the last 12 months or stroke, acute ischaemic heart disease or acute peripheral vascular disease in the last 6 months.
- 19) Hypersensitivity to any recombinant Escherichia coli-derived product (e.g., Infergen, Neupogen, Somatropin, and Actimmune) or known sensitivity to any of the products to be administered during dosing.
- 20) Currently enrolled in another investigational device or drug study or < 30 days since ending another investigational device or drug studies, or receiving other investigational agents.

- 21) Will have any other investigational procedures performed while enrolled in this clinical study.
- 22) Pregnant or breastfeeding, or planning to become pregnant or breastfeed during treatment or within 1 month after the end of treatment.
- 23) Female subject of childbearing potential is not willing to use, in combination with her partner, an acceptable method of effective contraception during treatment and for 1 month after the end of treatment (see annex 5 for additional contraception information). Females of childbearing potential should only be included after a negative pregnancy test.
- 24) Will not be available for protocol-required study visits, to the best of the subject's and investigator's knowledge.

[figure not shown]
	25) Any kind of disorder that, in the opinion of the investigator, may compromise the ability of the subject to give written informed consent and/or to comply with all required study procedures.26) Other serious comorbidities at investigator criteria.						
Primary objective	To evaluate the superiority of romiplostim plus dexamethasone vs dexamethasone alone in patients with newly diagnosed primary immune thrombocytopenia (ITP) in terms of sustained response off any ITP treatment (6 months (≥180 days) from treatment cessation, 6mSROT-50) and without WHO grade 2 or more bleeding.						
Secondary objectives	Multiple as described in Main Protocol						
Primary outcomes	To evaluate the difference between study achieving 6mSROT-50 at 6 months (180 da						
Secondary outcomes	Multiple secondary outcomes as detailed i	in Main Protocol.					
Investigational medicinal products (IMPs)	Dexamethasone (DEX) Romiplostim (ROM) (comparator drug) (investigational drug)						
Manufacturer	TAD Pharma, UK	Amgen, UK					
EU Certification, Labelling	Alcura Health, Spain	Alcura Health, Spain					
UK Import and Distribution	Alcura Health, UK	Alcura Health, UK					
Form	Uncoated tablets (4 or 12 per blister pack)	5mL single-use vial of sterile, preservative-free, lyophilised, solid white powder for resuspension					
Dose	40 mg daily: Investigational arm: X 4 days only in the first cycle and subcutaneous romiplostim weekly (ROM + DEX arm) for up to 12 months Comparator (DEX arm): Dexamethasone 40 mg daily x 4 days for up to 3 cycles every 14 to 28 days	Starting dose of 3 mcg/kg calculated on current body weight. Adjusting the following doses according to platelet counts.					
Route	Oral taken at home by participant	Subcutaneous injection					
Storage	Below 25°C. Protect from light and humidity.	2-8°C. Protect from light.					
Routine rescue medication	IVIg, platelet transfusion or prednisone. Tranexamic acid can be used but is not considered a rescue medication (excluded).						

3 Trial summary & schema

3.1 Trial schema/participant flow diagram

3.2 Organogram and data/drug flow diagram

3.3 Trial lay summary

RODEX is investigating Immune Thromobocytopenia (ITP), and an autoimmune disease where the immune system attacks important blood cells called platelets, which are essential for normal clotting. Patients with ITP have reduced numbers of platelets and are at risk of bleeding. A course of corticosteroids (steroids – a man-made version of a hormone the body makes naturally) is recommended as the first line of treatment for adults with newly diagnosed ITP. Most patients with ITP respond to corticosteroids with a rise in platelet count, but improvements are usually temporary and the majority of patients will relapse.

The objective of RODEX is to find out if a two-drug combination of corticosteroids (dexamethasone) plus a medicine called romiplostim is better than dexamethasone alone for first-line of treatment of ITP. Romiplostim is a thrombopoietin-receptor agonist (TPO-RA). Thrombopoietin (TPO) is the natural chemical that the body produces to tell the bone marrow to make more platelets. TPO-RA's are treatments that act like the body's own TPO to increase the number of platelets that are produced.

RODEX will recruit up to 126 adult (≥18 years) patients at up to 30 hospital sites in the European Economic Area (EEA), including Spain and Italy and up to 15 sites and 26+ participants in England, Wales and Scotland, UK. Adult patients will be eligible to take part if they meet the eligibility criteria, including recently diagnosed ITP with a low platelet count and no prior ITP treatment. Participants will be randomly allocated by a computer to receive a course of dexamethasone alone (control arm) or dexamethasone pus romiplostim (investigational arm) and followed up for up to 2 years (screening, day 1, week 8, week 12, month 6, month 12, and end of Study Visit) to find out if dexamethasone plus romiplostim can improve long-term treatment response and avoid bleeding. Study treatments and visits will vary slightly dependent on study arm.

4 Background

RODEX is an international CTIMP study. The lead Nation is Spain. Participants will be recruited in three nations within the EU: Spain, Italy and the UK via three different National Coordinators. Cardiff University is the UK National Coordinator and has delegated the responsible of Trial Management oversight in the UK to the Centre for Trials Research (CTR) within Cardiff University. Global regulatory approvals were in place in Spain and Italy prior to submission of the study to UK regulatory bodies. Refer to current English translation of Main Spanish Protocol for further background information.

5 Trial objectives/endpoints and outcome measures

Refer to Section 2 Synopsis and Section 3.1 for Trial Schema summarising patient flow, study objectives and outcome measures. Refer to Main Protocol for overall trial plan, design and rationale.

6 Risk assessment

The Main Protocol and this UK Protocol Addendum have approval from a UK Research Ethics Committee (REC; Wales REC1) that is legally recognised by the United Kingdom Ethics Committee Authority and the UK Medicines and Healthcare products Regulatory Agency (MHRA). Both documents will be submitted through the relevant permission system for global governance review dependant on the location of the lead UK site e.g. HCRW/HRA.

This clinical trial is to be conducted in compliance with the protocol, the EU Clinical Trial Regulation 536/2014 and Good Clinical Practice. In addition, in the UK, the trial will comply with all relevant UK clinical trial and data protection (General Data Protection Regulations Act 2020) and common law of consent regulations where relevant.

A Trial Risk Assessment and Data Protection Impact Assessment (DPIA) has been completed by the Sponsor to address study to identify the potential hazards associated with the trial and to assess the likelihood of those hazards occurring and resulting in harm. A UK-specific Risk Assessment and DPIA has been completed by the UK National Coordinator to address any additional risks specific to delivery of the trial in the UK in accordance with the MRC/DH/MHRA Joint project guidance document 'Risk-adapted approaches to the management of Clinical Trials of Investigational Medicinal Products' and includes:

• The known and potential risks and benefits to human subjects

• How high the risk is compared to normal standard practice

How the risk will be minimised/managed

This trial has been categorised as a TYPE B, where the level of risk is somewhat higher than the risk of standard medical care. A copy of the UK risk assessment may be requested from the CTR. The trial risk assessments will be used to determine the intensity and focus of monitoring activities by the Sponsor and UK National Coordinator.

7 Site and Investigator selection

This trial will be carried out at up to 15 participating sites within the UK (England, Wales and Scotland). The Sponsor will be responsible for site assessment approvals. The UK National Coordinator and CTR will manage, and have oversight for, the UK site set up green light procedure.

All sites who are interested in participating in the trial will be required to complete a registration form to confirm that they have adequate resources and experience to conduct the trial.

Before any Site can begin recruitment a Principal Investigator (PI) at each site must be identified and the PI and Site added to the Sponsor's UK insurance policy. The following documents must also be in place and copies sent to the CTR RODEX email account (see contact details on page 4):

Confirmation of Capacity and Capability (C&C) from R&D department following sharing of local information pack.

Favourable opinion of host care organisation/PI from Main Ethics committee

MHRA approval

Current Curriculum Vitae and Good Clinical Practice (GCP) training certificate of the Principal Investigator (PI)

Completed Site Staff Delegation Log and Roles and Responsibilities document

> Full contact details for all host care organisation personnel involved, indicating preferred contact

A copy of the most recent approved version of the UK Main and Pregnancy Participant Information Sheet(s) and Consent Form(s) on host care organisation headed paper

A copy of the most recent approved UK GP letter on host care organisation headed paper

➤ A set of laboratory normal ranges and laboratory certification/accreditation from the host care organisation laboratory being used for analyses

> Returned copy of the Self-Evident Correction Log signed by the PI.

Pharmacy confirmation that the Site has received the first shipment of IMP prior to opening

the site as specified in the Main Protocol

Executed UK Model Agreement for Non-Commercial Research (mNCA) between UK National

Coordinator/Sponsor Legal Representative and Site

Evidence of Site initiation by the CTR (conducted via teleconference)

Upon receipt of all the above documents, the Trial Manager will send written confirmation to the Site PI, lead Research Nurse, and lead Pharmacist as a minimum detailing that the centre is now ready and approved by the UK National Coordinator to recruit participants into the trial. This letter/email must be filed in each site's Investigator Site File (ISF). Along with the written confirmation, the site should

receive a study pack holding all the documents required to recruit into and deliver the study.

Occasionally during the study, amendments may be made to the study documentation listed above. The CTR will issue the site with the latest version of the documents as soon as they become available. It is the responsibility of the Site to ensure that sites obtain local R&D approval for the new documents.

8 Participant selection—see Spanish Protocol

9 Recruitment, Screening and registration – see Spanish Protocol

10 Withdrawal & lost to follow-up

Participants have the right to withdraw consent for participation in any aspect of the trial at any time. The participants care will not be affected at any time by declining to participate or withdrawing from the trial.

If a participant initially consents but subsequently withdraws from the trial, clear distinction must be made as to what aspect of the trial the participant is withdrawing from, the reason for withdrawal, and who made the decision to withdraw, for example patient and/or Clinician and/or Sponsor.

In all instances the event, date of withdrawal, reason(s) for withdrawal, aspect(s) of the trial being withdrawn from, and who made the decision, must be documented by the Site in the relevant section of the EDC System and the participants' hospital record.

For full details of withdrawal criteria, processes for handling withdrawals, lost to-follow up, permitted reasons for withdrawal, and data collection and other reporting requirements following withdrawal, refer to Section 8 of the Main Protocol.

For a summary of withdrawal options and associated actions see Section 9.1 below.

Queries relating to withdrawal of a participant should be forwarded to the CTR study email address in the first instance.

10.1 Summary of Withdrawal Options and Follow-Up Actions

In all cases participants will be followed up following RODEX visit/assessment schedule unless participant also explicitly withdraws their consent to do so, or other reason marked with an asterix (*) below.

Withdrawal	Primary Reason	Decision can be made by		ade by	Comments
From Trial		Patient	Local	Sponsor	
Treatment			Investigator		
Intervention	No response - treatment failure		X	X	Withdraw from ROM only, DEX only, or ROM + DEX
					Participant still followed up following RODEX visit/assessment schedule
	Patient choice	Χ			
	Adverse Event (AE)		X	X	AE will be followed up until AE resolved/stabilized. Complete and submit SAE notification form if considered an SAE.
	Intercurrent illness or worsening of a chronic condition		X	X	
	Diagnosis no longer ITP		X	Х	
	Pregnancy		Х		Female participants who become
	Intention to become pregnant	X	X		pregnant within 1 month of stopping treatment to be given pregnancy PIS/ICF and asked to provide optional consent for collection of pregnancy data. Complete and submit pregnancy notification form only if optional consent provided.
	Breastfeeding (lactation)		Х		Notify Sponsor/CTR by email. No separate data collection form or
	Intention to breast feed (lactate)	Х	Х		consent form to complete.
	Death *		Х		Complete death eCRF, and other relevant eCRF up to date of death.
	Lost-to-follow up *		X		If repeatedly fails to attend scheduled visits and is unable to be contacted by the study site following three telephone call attempts (where possible). Calls must bet documented in medical notes. Complete relevant eCRF up to date of lost-to-follow up.
	Patient non- compliance with treatment schedule		Х	Х	Report as a patient non- compliance
	Non-compliance with Protocol and/or study procedures		X	X	Report as a study non-compliance

Withdrawal From	Primary	Decision can be made by		Comments	
Other Trial Activities	Reason	Patient	Local Investigator	Sponsor	
Questionnaires					
SF-36 QOL	Other – e.g.	Χ			Report as a subject non-
FACTIT QOL	excessive	Χ			compliance if not returned
ITP PAQ QOL	burden	Χ			
ITP BAT		Χ			
Further study visits/assessments *		X			Report as a subject non- compliance if not attended unless participant deceased or lost-to-follow up
Further non-routine blood sample collection *		X			Report as a subject non-compliance.
					Any non-routine blood samples collected to provide study assessment data must be destroyed immediately following assessment following local destruction procedure and destruction evidenced in hospital notes and TSF and notified to CTR to meet UK HTA regulatory requirements.

Withdrawal from	Primary	Decision can be made by			Comments
Data Use	Reason	Patient	Local	Sponsor	
			Investigator		
Use of data already collected from	Other	X			Report as a protocol non- compliance. Note: data
medical					already entered onto EDC
notes/systems for					cannot prior to withdrawal
RODEX study					will not be destroyed.
purposes					
Further data collection from medical notes/systems following withdrawal *	Other	X			Report as a protocol non- compliance and stop participant treatment.
Use of data for future research	Other	X			

Withdrawal From	Primary	Deci	ision can be mad	le by	Comments
Whole trial	Reason	Patient	Local	Sponsor	
			Investigator		
	Screening		Х	Х	Patient can be re-screened
	failure -				once only.
	eligibility				
	criteria not				This type of withdrawal is not
	fulfilled				permitted once the patient
					has been randomised.
					Eligibility issues identified
					after randomisation must be
					reported as a study non-
					compliance.
	Non-		X	Х	Specify reason
	compliance				
	with Protocol				
	and/or study				
	procedures				
	Urgent Safety		X	X	Specify reason
	Measure				
	Early			Х	Specify reason
	termination				
	of study				
	Temporary			X	Specify reason
	suspension				
	of study				
	Other	X	X	X	Specify reason

Withdrawal From	Primary	Decision can be made by		Comments	
Provision of	Reason	Patient	Local	Sponsor	
mother/child			Investigator		
pregnancy reporting	Other	Χ			Only if consent provided via
data					UK Pregnancy ICF consent is
					withdrawn for any reason

11 Trial Intervention

See Spanish Protocol for treatment supply, storage and dosing, concomitant medication, rescue

medicine, study treatment stopping and dose adjustment rules, and other trial restrictions, including

pregnancy, lactation, breastfeeding, contraception.

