13.3.4 Pregnancy Reporting

[figure not shown]
Despite strict exclusion criteria around pregnancy, breast feeding and contraception and the anticipated low number of UK participants, there remains a very low risk that a participant (or for male participants, their female partner) will become pregnant during the study. If a pregnancy occurs, the participant (or their female partner where applicable), will be asked to provide **optional** consent via the study UK Pregnancy PIS/ICF for safety reporting of pregnancy data to the Sponsor and drug company (Amgen and/or TAD Pharma) where applicable.

Reported data may include confidential patient data belonging to the pregnant mother, and her unborn fetus and/or born child (including sex, date of birth and date of death).

This data will be collected and stored for a minimum of 25 years by the Sponsor in the interest of clinical trial regulatory compliance, and indefinitely by the drug manufacture under the mother's own consent, and parental consent provided on behalf of the born child where applicable, provided via the Pregnancy ICF.

The CTR will monitor for events of reporting confidential data belonging to a born child throughout the study, and liaise with the Sponsor to ascertain at the end of the participant follow up phase if/when there is a requirement for an application for CAG for CAGs251 and/or Scottish equivalent consent exemption as applicable (and continued REC approval) to support retention of data collected during childhood from a child born in England, Wales or Scotland beyond the date said child(ren) reach maturity to adulthood (age 16 years or over).

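### Section 10.1 triggers pregnancy consent and notification on a narrower window than Section 13.3.4 and, read literally, leaves out pregnancy during treatment

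*Protocol*

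**What the plan says.** Section 10.1 of the UK Protocol Addendum tabulates reasons for withdrawal and the action attached to each. In the block on withdrawal from trial treatment, one comment serves two adjacent rows, Pregnancy and Intention to become pregnant. It begins "Female participants who become" and continues "pregnant within 1 month of stopping treatment to be given pregnancy PIS/ICF and asked to provide optional consent for collection of pregnancy data". It then adds: "Complete and submit pregnancy notification form only if optional consent provided".

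Section 13.3.4, the section on pregnancy reporting, is wider. It recognises a low risk that a "participant (or for male participants, their female partner) will become pregnant during the study", and sets the action as follows: "If a pregnancy occurs, the participant (or their female partner where applicable), will be asked to provide" optional consent through the UK pregnancy information sheet and consent form. It names no limit related to the last dose.

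Exclusion criterion 22 in the Synopsis refers to a participant who is pregnant, breastfeeding or "planning to become pregnant or breastfeed during treatment or within 1 month after the end of treatment". Criterion 23 uses the same period for contraception. These are eligibility rules, not reporting rules.

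Sections 12 and 25 and the Synopsis put each participant's time on study at up to 24 months. Sections 10 and 13 refer to the Main Protocol for full withdrawal and safety-reporting procedures.

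**The concern.** The table in 10.1 is where a site looks when a participant stops treatment because of pregnancy. The natural case for that row is a woman found to be pregnant while on trial medication. The action beside it, however, is worded for conception after treatment has stopped. Elsewhere the addendum names the treatment period when it means to include it: criteria 22 and 23 do so, and so does the adverse event rule in Section 13.2, which runs from consent through treatment to 30 days after the last dose.

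The trigger matters because notification depends on consent. If the pregnancy consent form is not offered, consent cannot be given, and under 10.1 no form is submitted. At stake is the completeness of safety data on drug-exposed pregnancies and on those later in follow-up.

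**Working it through.** The plan gives no figure to reproduce. The check is a comparison of scope.

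**Reporting scope by section**

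| Source | Who | When |
|---|---|---|
| 10.1, literal reading | female participants | from stopping treatment to 1 month after |
| 10.1, generous reading | female participants | during treatment and to 1 month after |
| 13.3.4 | participants and female partners of male participants | any time during the study |

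**Inputs for sizing the gap**
- Romiplostim arm: treatment for up to 12 months (Synopsis, dose row).
- Dexamethasone arm: up to 3 cycles of 4 days, every 14 to 28 days (Synopsis, dose row).
- Time on study: up to 24 months.
- Assumption: 1 month is 30 days.

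**Romiplostim arm, full-length treatment**
- Literal 10.1 covers months 12 to 13, which is 1 month. Against 13.3.4 it leaves out 12 months on treatment and 24 − 13 = 11 months of later follow-up.
- Generous 10.1 covers months 0 to 13. It leaves out 24 − 13 = 11 months.

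**Dexamethasone arm, longest schedule**
- The third cycle starts on day 1 + 2 × 28 = 57 and ends on day 60. Adding 30 days gives day 90, about 3 months.
- Literal 10.1 covers about day 60 to day 90. It leaves out the first 60 days and what follows day 90.
- Generous 10.1 covers to day 90. It leaves out about 24 − 3 = 21 months if the participant stays on study for 24 months. If follow-up ends one year after the last dose, as another line of the Synopsis has it, it leaves out 12 − 1 = 11 months.

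**Test cases**
1. A woman conceives in month 4 of romiplostim. Section 13.3.4 has her asked for consent. Literal 10.1 does not reach her; generous 10.1 does.
2. A woman conceives 5 months after her last dose, still in follow-up. Section 13.3.4 has her asked for consent. Section 10.1 does not reach her on either reading.

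The second case shows that the mismatch does not depend on reading 10.1 literally. The first shows that the literal wording also drops exposure on treatment.

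**The case against.** The strongest reply is that 10.1 is only a summary of withdrawal options. It says what to do for one group and nowhere says that other pregnancies go unreported; its limiting word attaches to consent, not to timing. Section 13.3.4 is the dedicated rule, and it is wider rather than contrary. A site can follow both, and a case is lost only if the table is used alone. This stands. A reader might infer that the two sections give opposite instructions for the same participant, but the text does not support that.

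The shared comment also fits the second of its two rows well: a woman stops treatment because she intends to conceive, and does so within a month. One month may be meant as the outer limit of a window that includes treatment, in line with criteria 22 and 23. That is plausible and softens the literal reading. It does not remove the conflict for pregnancies later in follow-up.

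A reader might also count the absence of male participants' partners from 10.1 as a fault. It is not one. A partner's pregnancy is not listed as a reason to withdraw a participant from treatment, and 13.3.4 covers partners expressly.

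Finally, the Main Protocol holds the full reporting procedures and is not available here, so it cannot be said that any pregnancy would in fact go unreported. That limits the conclusion to a risk. It does not cure a mismatch between two sections of the same addendum, both of which rely on the same UK pregnancy consent form.

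**Conclusion.** The point holds in a narrow form. The trigger in 10.1 is narrower than the rule in 13.3.4 on any reading, and read literally it omits pregnancy during treatment. For a participant treated for 12 months and followed to month 24, the table covers 1 month on the literal reading and 13 on the generous one, against 24 under 13.3.4.

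The practical consequence is small. Section 13.3.4 itself calls the risk very low, and the UK plans for 26 or more participants. The documents give no expected number of pregnancies, so none is estimated. The primary endpoint, its analysis and the sample size are untouched.

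A reader might infer from the different treatment lengths that pregnancy data would not be comparable between arms. The addendum states no pregnancy endpoint and no such comparison, so that conclusion is not supported. The difference between the reporting rules and criteria 22 and 23 is not an error either, since an eligibility or contraception window need not equal a reporting window.

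The conclusion assumes that a site may act on the table without turning to 13.3.4, and that 13.3.4 means the participant's whole time on study.

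**What to change.** Reconcile 10.1 with 13.3.4. The simplest way is to replace the time limit in the shared 10.1 comment with a cross-reference to 13.3.4. Alternatively, state the same reporting window in both sections, with pregnancy during treatment explicitly included. The window should be expressed in terms the addendum already uses; 13.3.4 refers to the study period and does not define a start at first dose. Criteria 22 and 23 need not change.

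The cost is a wording change to one table comment. It needs no new form, consent document or visit. The downside is possibly one or two extra notification forms.
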